| Title of the Trial A prospective, observational long-term follow-up trial of kidney transplant patients treated with imlifidase or plasma exchange after an active/chronic active Antibody-Mediated Rejection (AMR) episode | |
| Co-ordinating Investigator [REDACTED] | |
| Trial Sites All sites, approximately 8-11 sites, in US, Europe and Australia, that have participated in trial 16-HMedIdeS-12 will be asked to participate. | |
| Planned trial period First subject first visit (FSFV) OCT/2020 Last subject last visit (LSLV) 3 years (+/- 4 months) after last subject's first visit in feeder trial | Clinical Phase Long-term prospective follow-up trial |
| Background and Scientific Justification for Conducting the Trial The aim of this trial is to collect data and provide a better understanding of the long-term outcome of imlifidase treatment on active or chronic active AMR in kidney transplant recipients. This is met by collecting data during extended follow up at 1, 2, and 3 years after treatment with either imlifidase or plasma exchange in trial 16-HMedIdeS-12. Data for parameters such as kidney graft survival, patient survival, kidney function, treatment of rebound of DSA and anti-drug antibodies will be collected. | |

Objectives

The primary objective of this trial is to evaluate kidney graft survival in subjects that have been treated with imlifidase or plasma exchange in association with AMR in trial 16-HMedIdeS-12 (referred to as the feeder trial).

Secondary objective(s) are to:

- Evaluate overall graft survival at Year 1 and 2
- Evaluate patient survival at Year 3
- Evaluate kidney function at Year 1, 2 and 3
- Evaluate DSA levels at Year 1, 2 and 3
- Evaluate anti-imlifidase IgG levels at year 1, 2 and 3 after
- Investigate the occurrence of AMR episodes after completed the feeder trial (classified according to Banff 2017 ([Haas et al. 2018](#)) or later version)
- Investigate the occurrence of other graft rejection episodes (classified according to Banff 2017 or later version)

Endpoints:

The primary endpoint of this trial is the overall graft survival, evaluated at Year 3.

Secondary endpoints of this trial are:

- Overall graft survival evaluated at Year 1 and 2
- Patient survival, evaluated at 3 years after start of treatment in feeder trial
- Kidney function, as evaluated by eGFR, S/P-creatinine and albumin/creatinine ratio in urine at 1, 2, and 3 years after start of treatment in feeder trial
- Proportions of subjects with presumed or biopsy proven AMR episodes (classified according to Banff 2017 or later version) within 3 years after start of treatment in feeder trial
- Proportion of subjects with presumed or biopsy-proven rejection episodes, (other than AMR episodes) classified according to Banff 2017 or later version) up to 3 years after start of treatment in feeder trial
- DSA levels at 1, 2, and 3 years after start of treatment in feeder trial
- Anti-imlifidase IgG at 1, 2, and 3 years after start of treatment in feeder trial

Methodology

This is an observational 3-year follow up trial. The trial will primarily evaluate kidney graft survival in subjects with active or chronic active AMR treated with imlifidase or plasma exchange. Subjects that have participated in trial 16-HMedIdeS-12 (called the feeder trial) will be asked to participate. The subjects will attend three follow up visits 1, 2, and 3 years after start of treatment in the feeder trial.

Trial Procedures/Assessments

At all visits, graft survival and information about graft rejection episodes will be assessed. Blood samples for graft function (creatinine and eGFR), and analysis of DSA and ADA will be collected as well as a urine sample for albumin/creatinine ratio. Information about patient survival and comorbidity (infections, malignancy, diabetes mellitus, cardiovascular events and comorbidity leading to worsening of kidney function) will be recorded.

Number of subjects

Up to 30 subjects will be included.

Diagnosis and main criteria for inclusion/exclusion

Inclusion criteria:

- Signed Informed Consent obtained before any trial-related procedures
- Willingness and ability to comply with the protocol
- Previous treatment with imlfidase or plasma exchange in trial 16-HMedIdeS-12

Exclusion criteria:

- Inability by the judgement of the investigator to participate in the trial for any other reason

Medicinal Product(s)

Not applicable

Duration of treatment

Each subject will be followed up 1, 2, and 3 years after start of treatment in feeder trial.

Statistical methods

This is a long-term observational trial and for the evaluation and presentation of data descriptive techniques will be used. The data from the clinical assessments will be summarized by time point and treatment group in the feeder trial. Summary statistics (n, arithmetic mean, standard deviation, median, minimum and maximum values) will be presented for continuous variables. Counts and, if relevant, percentages will be presented for categorical variables. The primary endpoint, overall graft survival will be evaluated and presented with Kaplan-Meier curves. There will be no formal statistical hypothesis or testing because of the observational nature of the trial. Since this is a long-term follow up trial to the 16-HMedIdeS12 trial, no sample size and associated power calculations has been made.

Protocol Revision History including Summary of Changes

| Protocol Version | Date | Including Amendment Type and No. | Overall Rationale for Changes |
|------------------|-------------|----------------------------------|---|
| 1.1 | 22-NOV-2021 | Non-substantial amendment No. 01 | 
• Change in CRO responsible for SAE/SUSAR reporting |
| 1.0 | 02-OCT-2020 | N/A | Initially approved protocol |

See [Appendix 1](#) “Clinical Study Protocol Amendment” for details of Amendment No. 01.

Table of Contents

| | |
|--|-----------|
| Signature page | 2 |
| Investigators and Clinical Trial Administrative Structure | 3 |
| Synopsis | 4 |
| Protocol Revision History including Summary of Changes | 7 |
| Table of Contents | 8 |
| List of Abbreviations..... | 12 |
| 1. Introduction..... | 13 |
| 1.1 Background | 13 |
| 1.2 Scientific Rationale | 14 |
| 1.3 Benefit/Risk Assessment..... | 14 |
| 2. Trial Objectives and Endpoints | 15 |
| 2.1 Objectives..... | 15 |
| 2.1.1 Primary Objective | 15 |
| 2.1.2 Secondary Objectives..... | 15 |
| 2.2 Endpoints | 15 |
| 2.2.1 Primary Endpoint | 15 |
| 2.2.2 Secondary Endpoints..... | 15 |
| 3. Investigational Plan..... | 16 |
| 3.1 Overall Trial Design..... | 16 |
| 3.1.1 Medical monitoring..... | 16 |
| 3.1.2 Interim Analysis..... | 16 |
| 3.2 Trial Schedule | 17 |
| 3.3 Planned Number of Trial Sites and Subjects | 17 |
| 3.4 End-of-Trial | 17 |
| 4. Trial Population | 18 |
| 4.1 Eligibility Criteria | 18 |
| 4.2 Inclusion Criteria..... | 18 |
| 4.3 Exclusion Criteria | 18 |
| 4.4 Restrictions..... | 18 |
| 4.4.1 Prohibited Therapy..... | 18 |
| 4.5 Discontinuation of Subjects | 18 |

| CTCAE | Common Terminology Criteria for Adverse Events |
| DSA | Donor-specific antibodies |
| EMA | European Medicines Agency |
| EOT | End of Trial |
| F(ab') ₂ | Antigen-binding fragments (two) of IgG linked by cysteine-bridge(s) |
| FDA | The Food and Drug Administration |
| GCP | Good clinical practice |
| eGFR | Estimated glomerular filtration rate |
| HLA | Human leukocyte antigen |
| ICH | International Council for Harmonisation of Technical Requirements for Pharmaceuticals for Human Use |
| IdeS | Immunoglobulin G degrading enzyme of Streptococcus pyogenes |
| IEC | Independent ethics committee |
| Ig | Immunoglobulin |
| Imlifidase | Immunoglobulin G-degrading enzyme of Streptococcus pyogenes , previously named HMED-IdeS or IdeS |
| IMP | Investigational medicinal product |
| IRB | Institutional review board |
| MedDRA | The Medical Dictionary for Regulatory Activities |
| MFI | Mean fluorescence intensity |
| N/A | Not applicable |
| RA | Regulatory authority |
| S/P- | Serum/plasma- |
| SAB-HLA | Single antigen bead assay |
| SAE | Serious adverse event |
| SAP | Statistical analysis plan |
| SDV | Source document verification |
| SUSAR | Suspected unexpected serious adverse reaction |
| TMF | Trial master file |

1. INTRODUCTION

1.1 Background

Antibody-mediated rejection (AMR) is one of the most challenging adverse events following kidney transplantation and a major cause of graft dysfunction and graft loss. AMR is triggered by donor-specific antibodies (DSA). DSA specifically target Human leukocyte antigen (HLA) molecules expressed by the transplant endothelium and cause complement-mediated damage and microvascular inflammation. Over time, features of chronic injury develop, e.g. transplant glomerulopathy. Transplant glomerulopathy is a known consequence of persistent DSA positivity which results in graft failure and return to dialysis with attendant consequences for the patient and financial costs for the health care system ([Gloor et al. 2008](#); [Jordan et al. 2010](#); [Lefaucheur et al. 2010](#); [Port et al. 1993](#); [Reinsmoen et al. 2008](#); [OPTN 2012](#)).

The time duration from the transplantation to the onset of clinical symptoms of AMR varies largely between individuals. The difference in time course of development of clinical symptoms of AMR might partly depend on whether the targeted HLA molecule has been previously encountered by the transplant recipient or not. An early AMR (< 30 days post-transplant) is commonly classified as active AMR and most often triggered by an immunological recall response with pre-existing DSA. A late AMR (> 30 days post-transplant) is classified as either active or chronic active AMR and is caused by either a recall DSA response or newly developing naïve immune response associated with de novo DSA production ([Schinstock et al. 2020](#)).

Therapies for AMR are limited ([Sellares et al. 2012](#)). Currently used therapies include high dose IVIg +/- rituximab, plasma exchange with low dose IVIg +/- rituximab, eculizumab, and a minimal experience with bortezomib. However, no therapy is currently approved, and patients are often treated with combination therapies that make analysis of efficacy of any one agent difficult. Thus, there is a large unmet clinical need for new therapies to treat AMR.

Imlifidase is an IgG-degrading enzyme of *Streptococcus pyogenes* that cleaves all four human subclasses of IgG with high efficacy and strict specificity. Cleavage of IgG generates one F(ab')₂- and one homodimeric Fc-fragment and efficiently neutralizes Fc-mediated activities of IgG, including complement activation and Fcγ receptor binding. The rapidity of the IgG cleavage by imlifidase is considered a major advantage as compared with plasma exchange, which often requires several rounds over several days to achieve a sufficient DSA reduction. Within a few hours after dosing, the entire pool of IgG is fully cleaved into F(ab')₂ and Fc fragments thereby creating a window where IgG levels are kept very low for approximately one week. Previous clinical trials supporting the rapid elimination of anti-HLA antibodies by imlifidase are summarized in [Table 1](#).

The short-term efficacy and safety of imlifidase in active and chronic active AMR is currently being investigated in an ongoing randomized, open-label, multi-centre trial, using plasma exchange as active control (16-HMedIdeS-12). A total of 30 subjects will be included, 20 in the imlifidase arm and 10 in the plasma exchange arm. In brief, the primary objective is to investigate the efficacy of imlifidase in removing DSA in patients who are experiencing an

AMR episode after kidney transplantation. Key efficacy outcome measures such as kidney function and graft survival will be followed as secondary endpoints, as will DSA levels, up to 180 days after treatment.

While a rapid removal of DSA by imlifidase might be expected, DSA is likely to rebound unless well-controlled by concomitant immunosuppressive therapy. Therefore, there is a need to also address the long-term benefit of imlifidase in AMR.

Table 1. Summary table of clinical studies with imlifidase showing rapid effect on anti-HLA antibodies/DSA.

| Trial No. / EudraCT No./ IND No. | Phase / Subjects | Main objectives |
|--|--------------------------------------|---|
| 13-HMedIdeS-02 / 2013-005417-13 | II / Patients with CKD N= 8 | Efficacy in patients with CKD defined as imlifidase dosing scheme resulting in HLA antibody levels acceptable for transplantation, within 24 h from dosing. Safety in the transplantation setting. |
| 13-HMedIdeS-03 / 2014-000712-34 | II / Patients N=10 | Safety in the transplantation setting. Efficacy defined as HLA antibody levels acceptable for transplantation. |
| 14-HMedIdeS-04 / EudraCT: NA IND 124301 (Investigator initiated trial) | II / Patients N=17 | Safety in combination with Cedars Sinai's "standard protocol" for desensitization of highly sensitized patients. Efficacy in prevention of ABMR. |
| 15-HMedIdeS-06 / 2016-002064-13 IND: 128074 | II / Patients N=19 | Efficacy in creating a negative crossmatch test. Safety in the transplantation setting. |

1.2 Scientific Rationale

The aim of this trial is to collect data and provide a better understanding of the long-term outcome of imlifidase treatment on active or chronic active AMR in kidney transplant recipients. This is met by collecting data during extended follow up at 1, 2, and 3 years after start of treatment with either imlifidase or plasma exchange in trial 16-HMedIdeS-12. Data for parameters such as kidney graft survival, patient survival, kidney function, treatment of rebound of DSA and anti-drug antibodies will be collected.

1.3 Benefit/Risk Assessment

The subjects included in this trial have been treated with imlifidase or plasma exchange in the feeder trial. The current trial is performed to collect long-term follow up data on graft function. No IMP will be administered in this trial. Most of the assessments performed under the current protocol are already part of the follow up within standard of care for these subjects and consequently they will not be exposed to any additional risk.

2. TRIAL OBJECTIVES AND ENDPOINTS

2.1 Objectives

2.1.1 Primary Objective

The primary objective of this trial is to evaluate kidney graft survival in subjects that have been treated with imlifidase or plasma exchange in association with AMR in the trial 16-HMedIdeS-12 (referred to as the feeder trial).

2.1.2 Secondary Objectives

The secondary objectives of this trial are to:

- Evaluate overall graft survival at Year 1 and 2
- Evaluate patient survival at Year 3
- Evaluate kidney function at Year 1, 2 and 3
- Evaluate DSA levels at Year 1, 2 and 3
- Evaluate anti-imlifidase IgG levels at Year 1, 2 and 3
- Investigate the occurrence of AMR episodes after completion of the feeder trial (classified according to Banff 2017 ([Haas et al. 2018](#)) or later version)
- Investigate the occurrence of other graft rejection episodes (classified according to Banff 2017 or later version)

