2.2.2 Secondary Endpoints

Secondary endpoints of this trial are:

- Overall graft survival evaluated at Year 1 and 2
- Patient survival, evaluated at 3 years after start of treatment in feeder trial
- Kidney function, as evaluated by eGFR, S/P-creatinine and albumin/creatinine ratio in urine at 1, 2, and 3 years after start of treatment in feeder trial
- Proportions of subjects with presumed or biopsy proven AMR episodes (classified according to Banff 2017 or later version) within 3 years after start of treatment in feeder trial
- Proportion of subjects with presumed or biopsy-proven rejection episodes, (other than AMR episodes) (classified according to Banff 2017 or later version) up to 3 years after start of treatment in feeder trial
- DSA levels at 1, 2, and 3 years after start of treatment in feeder trial
- Anti-imlifidase IgG at 1, 2, and 3 years after start of treatment in feeder trial

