6.1.2 Year 1, Year 2, and Year 3 (End-of-Trial)

The following visit windows applies:

Year 1: (+/- 2 months)

Year 2 and Year 3 (End-of-Trial): (+/- 4 months)

The following activities and assessments will be performed:

- Assessment of graft survival. For subjects with graft loss since last visit in the feeder trial or screening (if screening is done at a separate visit), date, reason for graft loss, medical history, and root cause will be recorded.
- Record patient survival (if applicable, date and cause of death)
- Collect information about graft rejection episodes, (classified by Banff 2017 or later). For-cause biopsies together with contemporaneous local DSA analyses, kidney function parameters (P-creatinine, U-albumin/creatinine ratio) and treatments (e.g. plasma exchange and IVIg) will be collected to assess the rejection episodes.
- Record information from standard of care biopsies, if available
- Sample for S/P-creatinine will be drawn (eGFR will be calculated by the Sponsor)
- Collect urine sample for measurement of albumin/creatinine ratio
- Sample for HLA antibodies, including DSA, and ADA will be drawn
- Record comorbidity such as infections, malignancy, diabetes mellitus, cardiovascular events and comorbidity leading to worsening of kidney function, that occurred after end of trial in feeder trial
- Record current immunosuppressive medications
- Record treatment with dialysis
- AEs related to trial procedure or IMP in feeder trial will be recorded, see section 9

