12.4.4 Proportion of subjects with rejection episodes

Proportion of subjects with presumed or biopsy-proven AMR episodes (classified according to Banff 2017 or later) and proportion of subjects with biopsy-proven rejection episodes, (other than AMR episodes) within 3 years after start of treatment in feeder trial will be listed and summarised by treatment group.

12.4.5 DSA level at 1, 2, and 3 years after start of treatment in feeder trial

DSA levels (measured using SAB-HLA assay) 1, 2 and 3 years after start of treatment in feeder trial will be summarized, listed, and presented graphically.

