4.4.2.4 Proportion of patients with rejection episodes

Proportion of patients with presumed or biopsy-proven AMR episodes (classified according to Banff 2017 or later) and proportion of patients with biopsy-proven rejection episodes, (other than AMR episodes) within 3 years after start of treatment in feeder trial will be listed and summarised by treatment group.

4.4.2.5 DSA level at 1, 2, and 3 years after start of treatment in feeder trial

DSA levels (measured using SAB-HLA assay) at 1, 2 and 3 years after start of treatment in the feeder trial will be summarized, listed, and presented graphically. The individual plots, will include sum of DSA as a separate line. Mean plots will display the mean of "sum of DSA".

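### The AMR objective starts after the feeder trial, but the planned proportion counts from the start of feeder treatment, with no stated data source for its first 180 days

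*Protocol*

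**What the plan says.** **Objective.** Protocol 2.1.2 and SAP 1.1.1 both ask to "Investigate the occurrence of AMR episodes after completion of the feeder trial"; the protocol synopsis is worded similarly. The adjacent objective on other types of rejection carries no such limit, so the mismatch is specific to AMR.

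**Endpoint.** Protocol 2.2.2 takes the share of patients with an AMR episode, whether presumed or confirmed by biopsy ("classified according to Banff 2017 or later version) within 3 years after start of treatment in feeder trial". SAP 1.1.2 repeats this.

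**Analysis.** SAP 4.4.2.4 plans the "Proportion of patients with presumed or biopsy-proven AMR episodes (classified according to Banff 2017 or later"). It uses the same time frame as Protocol 12.4.4: "within 3 years after start of treatment in feeder trial will be listed and summarised by treatment group".

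**Feeder follow-up.** Protocol 1.1 says that kidney function and graft survival are followed in the feeder trial, "as will DSA levels, up to 180 days after treatment".

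**Collection.** At the Year 1, 2 and 3 visits, Protocol 6.1.2 says to "Collect information about graft rejection episodes, (classified by Banff 2017 or later"), with no date from which to look back. In the same list, comorbidity is limited to what arose "that occurred after end of trial in feeder trial", and graft loss is taken from the last feeder visit or from screening. The flow charts (Protocol 6.2, SAP 2.1) show no collection of rejection episodes at screening.

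**Source and output.** SAP 4.1.2 takes baseline values from the feeder trial. SAP 4.4 says which patients are analysed, not which database supplies their events. The titles of Table 14.2.4 and Listing 16.2.4 give no time window.

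**The concern.** The objective and the proportion meant to serve it start about six months apart. A reader who takes Table 14.2.4 as the answer to the objective would be reading a figure that is designed to include the feeder period.

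The figure may also fall short of its own definition. It is meant to start at feeder treatment, but this trial gathers rejection episodes only from Year 1 and gives sites no look-back date. One site could record from the start of feeder treatment and another from the end of the feeder trial. Nothing says whether feeder records fill the gap. A proportion described as covering three years could then cover roughly month 6 to month 36 for some patients and the full period for others.

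Counting from the start of feeder treatment also needs a rule for the index episode, because every patient was being treated for AMR at that moment. Neither document gives one.

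**Working it through.** The documents state no AMR rate, power or sample-size figure, so there is no planned number to reproduce. The check compares the windows and then sizes the gap.

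**1. Windows side by side**

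| Item | Starts | Ends |
|---|---|---|
| Objective (Protocol 2.1.2, SAP 1.1.1) | Completion of feeder trial | Not stated |
| Endpoint (Protocol 2.2.2, SAP 1.1.2) | Start of feeder treatment | 3 years |
| Analysis (Protocol 12.4.4, SAP 4.4.2.4) | Start of feeder treatment | 3 years |
| Collection at visits (Protocol 6.1.2, SAP 2.1) | Not stated | Each visit to Year 3 |
| Table 14.2.4, Listing 16.2.4 (SAP 9.1, 9.2) | Not stated | Not stated |

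The endpoint and analysis agree; the objective is the outlier. Its start is also undefined for some patients, because Protocol 4.2 admits those who did not finish feeder follow-up.

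**2. Share of the window in dispute**

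Inputs: 180 days (Protocol 1.1) and 3 years.
180 / (3 × 365.25) = 180 / 1095.75 = 16.4%.

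SAP section 6 records that the trial was stopped early, in January 2023. For a patient whose observation ended before Year 3 the share is larger. For example, with 2 years observed it is 180 / 730.5 = 24.6%.

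**3. Effect of one patient**

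Inputs: 20 and 10 patients at full enrolment (Protocol 12.6). A patient whose only AMR episode falls in days 0–180 counts in one window and not in the other:
- imlifidase: 1/20 = 5.0 points
- plasma exchange: 1/10 = 10.0 points
- total: 1/30 = 3.3 points

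Lower enrolment makes each step larger.

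**4. Illustration under assumed rates**

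This is not an expected shift. Assume episodes arise at a constant rate, follow-up is complete, and a proportion p of patients has at least one episode in three years. The proportion with an episode after day 180 is 1 − (1 − p)^(1 − 0.164).

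| Assumed p | After day 180 | Difference |
|---|---|---|
| 10% | 8.4% | 1.6 points |
| 30% | 25.8% | 4.2 points |
| 50% | 44.0% | 6.0 points |

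In patients, the largest difference is 0.060 × 20 = 1.2 in the imlifidase arm and 0.060 × 10 = 0.6 in the plasma exchange arm. If early episodes were more common than a constant rate implies, the difference would be larger; the documents give no basis for choosing how much.

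**The case against.** **The planned window is not in doubt.** The endpoint and analysis text of both documents agree, and an objective does not define the computed quantity. This stands. A reader might infer that the analyst is free to choose between two windows, but the documents do not support that. What remains is that the one window chosen does not answer the objective.

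**Nothing says that the first six months are left out.** A reader might infer that the three-year proportion does omit them. The documents do not show this: rejection episodes have no look-back limit, unlike comorbidity in the same list, and the flow-chart footnote has standard-of-care biopsies recorded whenever they were taken. The supportable statement is that the period may be under-covered.

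**The protocol does not say that the arms differ early.** A reader might reason from the expected return of DSA after imlifidase that including or dropping six months would change the comparison between arms. Protocol 1.1 makes the rebound conditional on immunosuppression, gives no timing and makes no claim about AMR by arm. That inference is not supported.

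**The feeder database may not hold these episodes.** Protocol 1.1 names kidney function, graft survival and DSA as feeder outcomes, not rejection. This stands, so any use of feeder data has to be conditional.

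**The index episode began before treatment.** Its onset therefore lies outside a window that opens at treatment. This is right as far as it goes, but persistence of that episode versus a new one is still left open.

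**The consequence is limited.** There is no hypothesis test (SAP 4.1.1), and all data are listed by patient. This also stands, although a listing cannot show episodes that were never collected.

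**Conclusion.** The mismatch is real and appears in both documents. The proportion in Table 14.2.4 follows the endpoint and leaves the AMR objective without a matching result. Coverage of its first 180 days, 16.4% of the window, is not assured by any stated look-back or data source.

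The size is modest: one reclassified patient moves an arm by 5 points (n=20) or 10 points (n=10), assuming full enrolment. With no AMR rate in the documents, neither the amount nor the direction of any effect on the comparison between arms can be stated. Since the endpoint is secondary and purely descriptive, this is a correction to make for a readable result, not a threat to the trial's main conclusion.

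**What to change.** In SAP 4.4.2.4, and in Table 14.2.4 and Listing 16.2.4, report two rows with the window in each label:

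- **(a) Start of feeder treatment to Year 3**, which is the endpoint.
- **(b) Day 180 to Year 3**, which is the objective. For patients who did not complete the feeder trial, start at their last feeder visit.

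For row (a), take episodes in days 0–180 from the feeder database if they were recorded there, and otherwise from what was recorded by look-back at Year 1. If neither covers the period, label the row as incomplete.

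Count only episodes with a new diagnosis date after the start of feeder treatment, so that the index AMR is not counted. This assumes that each episode carries a diagnosis date, which the visit list does not spell out. Flag in the listing any later finding that may be a continuation of the index episode.

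Align the objective with the two rows. Protocol 13.3 already provides for describing SAP changes in the trial report.

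The cost is one extra row and a check of what the feeder database holds. No new patient visits or samples are needed.
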